### **6.3. Other Endpoints**

#### **6.3.1. PRO endpoints (Cohort A only)**

All PRO analyses will be performed based on the FAS.

##### **6.3.1.1. PRO instruments**

Patient-reported outcomes will be collected using the following instruments: European Organization for Treatment of Cancer Quality of Life Questionnaire (EORTC QLQ-C30), non-muscle invasive bladder cancer symptoms (NMIBC24), health status in participants with NMIBC (EQ-5D-5L), disease severity (PGIS), patient global impression of change (PGIC), treatment administration burden (PTAB), and treatment satisfaction questionnaire (TSQ).

##### **6.3.1.2. PRO scoring**

The EORTC QLQ-C30, NMIBC24, and EQ-5D-5L will be scored according to their respective user guides. The current version at the time of analysis, of UK weights, will be

used to construct the index values of the EQ-5D-5L. For the EORTC QLQ-C30, EORTC QLQ NMIBC24, and EQ-5D-5L, missing items will be handled per the respective scoring manuals of each questionnaire. For the PGIS, PGIC, TSQ, and PTAB there will be no adjustments for missing data.

PGIS, PGIC, PTAB, and TSQ questionnaire items will be analyzed separately, items within each questionnaire will not be combined or scored.

#### **6.3.1.3. Instrument completion rates**

For each treatment arm in Cohort A, at each time point the number and percentage of participants who complete each of the EORTC QLQ-C30, NMIBC24, EQ-5D-5L, PGIS, PGIC, PTAB, and TSQ will be summarized.

#### **6.3.1.4. Descriptive Summary**

Separate tables for each questionnaire for Cohort A will be used to summarize the mean, SD, median, range and 95% CI of absolute scores and change from baseline of the total, all subscales of the EORTC QLQ-C30, NMIBC24, EQ-5D-5L (index and VAS) at each time point. A line chart depicting the means along with 95% CI bars over time will be provided for each scale in each Cohort A treatment arm.

For the PTAB, PGIS, PGIC, and TSQ, summary statistics (number and percentage) will be provided for each item, by treatment arm in Cohort A at each time point.

A figure will be provided for the cumulative patient disposition by treatment arm in Cohort A per PRO assessment window for all scheduled assessments using the following categories:

- PRO assessment expected;
- PRO assessment not expected due to lack of efficacy;
- PRO assessment not expected due to death;
- PRO assessment not expected due to other reasons.

#### **6.3.1.5. Health Status**

For the EQ-5D-5L, for each treatment arm in Cohort A, the number and percentage of participants reported having “none”, “slight”, “moderate”, “severe”, or “extreme/unable” problems at each time point will be calculated.

#### **6.3.1.6 Random Coefficient Models**

Random coefficient models will be carried out in Cohort A for the EORTC QLQ-C30 and NMIBC24 (all domains, subscales and symptoms), EQ-5D-5L (Index), and EQ-VAS using PROC MIXED. Outcomes are post-baseline scores and change scores and the predictors are the corresponding baseline PRO score, treatment, time (treated as a continuous variable), and treatment-by-time interaction. Intercept and time are considered as random effects particular to each participant. All available data for each participant prior to the end of therapy should be used in the analyses. All parameter estimates should be obtained using restricted

maximum likelihood. The unstructured covariance structure should be used to define covariance between random effects (using option “Type=UN” as a part of the RANDOM statement in PROC MIXED). For the degrees-of-freedom calculations the Kenward and Roger algorithm should be used (using option ddfm = kr”) as a part of the MODEL statement in PROC MIXED).

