Urinalysis	X	X*		X						X		X**	Collect sample prior to each BCG administration as indicated, including: *during the re-induction, as applicable (Cycles 4 and 5) **during Cycles 19 and 25. As clinically indicated during other cycles. See Section 10.2 for the list of the tests.
Pregnancy Test	X	X	X	X	X	X	X	X	X	X	X	X	A negative highly sensitive test is required prior to study intervention dosing on Day 1 of all cycles. Results must be available for review prior to dosing. See Section 8.2.8 and Section 10.4. Pregnancy testing per local guidelines.
ACTH & Thyroid Function Test			X			X			X			X*	*Completed on Day 1 of Cycles 15, 18, 21, 24, 25.
BCG Administration (Arms A & C)	X*#	X*		X#						X#		X#	Follow calendar cycle for dosing, not the schedule. See Section 6.1.2 for details. On days when BCG and PF-06801591 are both administered, BCG is administered first. *Re-induction period: See Section 4.1 for participants who may meet criteria for re-induction. Suggested instillations on C4D1, C4D8, C4D15, C4D22, C5D1, and C5D8. Maintenance will then begin on C7D1. If TURBT is performed, BCG re-induction schedule should be modified according to the product label. #Maintenance BCG schedule: D1, D8, D15 of Cycles 4, 7, 13, 19, and 25.
PF-06801591 Administration (Arms A & B)	X	X	X	X	X	X	X	X	X	X	X	X	Administer subcutaneously Q4W up to Cycle 25. See Section 6.1.2.

Maintenance Period: Cycles 4 to 25 (Cycle = 4 Weeks) for participants without re-induction BCG Re-induction Period for Participants Who Receive BCG Re-induction: Cycles 4-6 ; Maintenance Period: Cycles 7 to 25													
	C4D1	C5D1	C6D1	C7D1	C8D1	C9D1	C10D1	C11D1	C12D1	C13D1	C14D1	C15D1 thru C25D1	Notes
Visit Window (Days)	±7	±7	±7	±7	±7	±7	±7	±7	±7	±7	±7	±7	
Disease Assessments													
CT or MRI	As clinically indicated												
Cystoscopy with or without Biopsy	X			X			X			X		X*	Participants with CIS at randomization who do not achieve a CR within 6 months of initiating study intervention will discontinue study treatment and enter the post-treatment follow-up period. Cystoscopy with or without tumor biopsy; ±7 days allowed for on-treatment assessment. Same equipment and methods by the same study staff should be used for the duration of the study whenever possible. See Section 8.1.1.1. * Completed every 12 weeks.

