Cytology	X			X			X			X		X*	Urine cytology; ±7 days allowed for on-treatment assessment. Same equipment and methods by the same study staff should be used for the duration of the study whenever possible. See Section 8.1.1.2. *Completed every 12 weeks.
Patient Reported Outcomes (PROs)													
EORTC-QLQ-C30, EORTC NMIBC24,	X	X	X	X			X			X		X*	All PROs will be completed prior to clinical assessments and procedures and treatment administration, with the exception of the PTAB, which will be completed immediately after treatment administration. Laboratory assessments may be done prior to PROs if laboratory assessments are done on a date prior to the rest of the study visit. See
EQ-5D-5L	X	X	X	X			X			X		X*	
PGIS	X	X	X	X			X			X		X*	
PGIC	X	X	X	X			X			X		X*	
TSQ	X			X						X		X*	

Maintenance Period: Cycles 4 to 25 (Cycle = 4 Weeks) for participants without re-induction BCG Re-induction Period for Participants Who Receive BCG Re-induction: Cycles 4-6 ; Maintenance Period: Cycles 7 to 25													
	C4D1	C5D1	C6D1	C7D1	C8D1	C9D1	C10D1	C11D1	C12D1	C13D1	C14D1	C15D1 thru C25D1	Notes
Visit Window (Days)	±7	±7	±7	±7	±7	±7	±7	±7	±7	±7	±7	±7	
PTAB	X			X						X		X*	Section 8.1.2. PROs will be administered in the following order: EORTC QLQ-C30, EORTC NMIBC24, EQ-5D-5L, PGIS, PGIC, TSQ, PTAB. *Completed on Day 1 of Cycles 19 and 25.
Immunogenicity, Pharmacokinetic, and Pharmacodynamic Biospecimen													
Immunogenicity	X		X		X		X			X			Collected pre-dose at each time point for Anti-PF-06801591 Antibody (ADA/NAb) measurement. See Section 8.8.3. Arms A and B only.
Pharmacokinetics	X		X		X		X			X			Collected pre-dose at each time point for PK analysis of PF-06801591. All efforts should be made to obtain PK samples within 2 hours prior to PF-06801591 dosing. See Section 8.5. Arms A and B only.
Whole blood biomarkers	X		X		X		X			X			See Section 8.8.
Plasma and Serum Biomarker Sample	X		X		X		X			X			See Section 8.8.

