8.1.2. Patient Reported Outcomes (PROs)

All PRO questionnaires will be administered electronically and will be completed during the visit prior to any other clinical assessments and study procedures, with the exception of the PTAB which will be completed immediately after the study intervention. If laboratory assessments are done on a date prior to the main visit date, PROs may be completed as the first assessment at the main visit. PROs will be administered in following order: EORTC QLQ-C30, EORTC NMIBC24, EQ5D5L, PGIS, PGIC, TSQ, and PTAB.

As of 12 September 2022, PROs will not be required for Cohort B1 and B2 participants.

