9.4.3.1. Patient Reported Outcomes

The EORTC QLQ-C30 & NMIBC24, and EQ-5D-5L will be scored according to their respective user guides.

For the EORTC QLQ-C30 & NMIBC24 and EQ-5D-5L, missing items will be handled per the respective scoring manuals of each questionnaire. For the PGIS, PGIC, PTAB, and TSQ, there will be no adjustments for missing data.

Summary statistics [mean (and SD), median, range and 95% CI] of absolute scores will be reported for all of the subscales of the EORTC QLQ-C30 & NMIBC24, PTAB, and the EQ-5D-5L. The mean change of absolute scores from baseline (and 95% CI) will also be assessed. Longitudinal mixed effect-model analyses will be used to assess change from baseline in the EORTC QLQ-C30 & NMIBC24 domains and EQ-5D-5L between the 3 treatment arms in Cohort A. Additional exploratory analyses may be performed, such as analyses of time to deterioration or improvement, if warranted.

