**3.4.2. Baseline characteristics**

In Cohort A, randomization is stratified by the following, as recorded in the interactive response technology (IRT):

- Presence of carcinoma in situ at randomization (yes vs no);
- Geography (US vs Western Europe and Canada vs ROW).

The primary analyses for Cohort A of EFS and OS will be stratified by these randomization stratification factors.

Other baseline characteristics (including demographics, disease history, and prior anti-cancer therapies) are described in [Section 6.5.1](#). These baseline characteristics are not planned to be included as stratification variables or covariates in statistical models unless otherwise specified in [Section 6](#).

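### The only between-arm PRO model is a straight line in time, which heavily dilutes a short-lived effect of maintenance BCG; separately, it leaves out the randomization strata

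*SAP*

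**What the plan says.** **Model.** The random coefficient models in SAP 6.3.1.6 cover QLQ-C30, NMIBC24, the EQ-5D-5L index and EQ-VAS. Predictors are "the corresponding baseline PRO score, treatment, time (treated as a continuous variable), and treatment-by-time interaction", with a random intercept and slope per participant. There is no visit factor, no curvature term and no stratum term, and no contrast is named. On the data to be used: "All available data for each participant prior to the end of therapy should be used in the analyses".

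**Protocol.** Section 9.4.3.1 states: "Longitudinal mixed effect-model analyses will be used to assess change from baseline in the EORTC QLQ-C30 & NMIBC24 domains and EQ-5D-5L between" the three arms. It does not fix the form of time.

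**BCG dosing.** The Schedule of Activities gives, for Arms A and C, "Maintenance BCG schedule: D1, D8, D15 of Cycles 4, 7, 13, 19, and 25". Section 4.1.1 defines Arm B as induction only.

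**Questionnaires.** QLQ-C30, NMIBC24 and EQ-5D-5L are scheduled after baseline on Day 1 of Cycles 2 to 7, 10 and 13, and then "Completed on Day 1 of Cycles 19 and 25". Under Protocol 8.1.2 they "will be completed during the visit prior to any other clinical assessments and study procedures", so on a dosing day they precede the dose, "with the exception of the PTAB, which will be completed immediately after treatment administration". All three are also collected at the end-of-treatment (EOT) visit, which falls within 7 days of the last dose.

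**Descriptive output.** SAP 6.3.1.4 gives scores and changes from baseline by arm at each time point with 95% CIs, line charts by arm, and counts for PTAB items.

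**Strata.** SAP 3.4.2: "The primary analyses for Cohort A of EFS and OS will be stratified by these randomization stratification factors". It makes no such commitment for PROs.

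**The concern.** Maintenance BCG consists of three weekly instillations, separated by months. If symptoms rise during a course and then settle, the difference between arms is a spike rather than a trend, and a straight line cannot follow a spike. Nearly all scheduled visits fall long after the previous course, so one informative visit is averaged with nine others.

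Health-related quality of life is a secondary objective, and Protocol 4.2 names symptoms and treatment burden as important considerations. Maintenance BCG is what separates Arm A from Arm B. A modest transient cost of maintenance could therefore leave almost no trace in the only modelled comparison. No efficacy conclusion is affected.

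**Working it through.** **1. The plan's own gaps.** SAP 6.5.3.4 uses 70 days from C4D15 to C7D1 and 154 days from C7D15 to C13D1. With 28-day cycles: 3×28 − 14 = 70 and 6×28 − 14 = 154. Both reproduce.

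**2. Gap from the last scheduled maintenance dose to each questionnaire.** Study day = 28×(cycle − 1) + day.

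| Visit | Week | Study day | Last maintenance dose | Gap (days) |
|---|---|---|---|---|
| C5D1 | 16 | 113 | C4D15 = 99 | 14 |
| C6D1 | 20 | 141 | C4D15 = 99 | 42 |
| C7D1 | 24 | 169 | C4D15 = 99 | 70 |
| C10D1 | 36 | 253 | C7D15 = 183 | 70 |
| C13D1 | 48 | 337 | C7D15 = 183 | 154 |
| C19D1 | 72 | 505 | C13D15 = 351 | 154 |
| C25D1 | 96 | 673 | C19D15 = 519 | 154 |

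C2D1, C3D1 and C4D1 precede any maintenance dose. The EOT visit is 0-7 days after C25D15 for Arm A and C completers, but falls outside the model if the data restriction is read literally.

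**3. What a straight line does.** The ten post-baseline visits are at weeks 4, 8, 12, 16, 20, 24, 36, 48, 72 and 96. Their mean is 33.6 and Sxx = 8166.4. With complete data and a random intercept and slope, generalized and ordinary least squares agree (checked with three sets of variances). A difference d at visit week s contributes to the fitted difference at week t:

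d × [1/10 + (s − 33.6)(t − 33.6)/8166.4].

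*Difference at C5D1 only (s = 16):*
- Week 16: 0.1 + 17.6²/8166.4 = 0.138, so 0.14d; about 86% is lost.
- Week 96: 0.1 − 17.6×62.4/8166.4 = −0.034, so −0.03d.

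*Difference from C5D1 onward (seven of ten visits):* mean 0.7, slope = 76.8/8166.4 = 0.0094 per week.
- Week 16: 0.7 − 17.6×0.0094 = 0.53d.
- Week 48: 0.7 + 14.4×0.0094 = 0.84d.
- Week 96: 0.7 + 62.4×0.0094 = 1.29d.

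**4. Sensitivity.** For the C5D1-only pattern, using visit number instead of weeks gives 0.127d at week 16. Linear attrition to 70%, 50% or 30% observed at C25 gives 0.134-0.136d. With the same attrition the sustained pattern gives 0.49-0.51d at week 16 and 1.37-1.62d at week 96.

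**5. Power (assumptions, not in the documents).** Two-sided 0.05. For a visit-specific comparison with SD 20-25 and 233-333 evaluable per arm, power at C5D1 is 0.58-0.90 for 5 points and at least 0.99 for 10. For the linear model with 333 per arm (intercept variance 250, slope variance 0.02, covariance −0.5, residual variance 200), a C5D1-only difference of 5 or 10 points is estimated at week 16 as 0.7 or 1.4 points, with power about 0.08 or 0.19. Under the same variances, the joint 2-df test has power about 0.95 for a sustained 5-point difference.

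**6. Strata.** Adding a balanced stratum term while keeping time linear leaves the retained share at 0.138. If strata explain a further 2-10% of variance (assumed), the standard error falls by 1 − √(1 − R²): 1% at R² = 0.02 and 5% at R² = 0.10.

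**The case against.** **The model complies and PROs are not alpha-controlled.** True. A random coefficient model is a longitudinal mixed model, and PROs lie outside the four hypotheses tested with type I error control. The point is about what the analysis can estimate, not about a breach of the protocol.

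**A reader might infer that C5D1 is the only questionnaire near a maintenance dose.** The documents do not support that. EOT questionnaires come 0-7 days after the last dose, and PTAB is completed straight after dosing on Day 1 of each maintenance cycle. C5D1 is unique only among scheduled on-therapy QLQ-C30, NMIBC24 and EQ-5D-5L visits. PTAB covers administration pain and time burden, not symptoms over the following weeks.

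**A reader might infer that the plan cannot show maintenance burden.** That is too strong. By-visit summaries and charts will display C5D1 by arm with CIs, and the linear model would pick up a sustained effect. What is missing is a baseline-adjusted between-arm estimate at the visit.

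**A reader might blame the missing strata for the smoothing.** They do not cause it, as step 6 shows. Nor do they contradict SAP 3.4.2, which commits only EFS and OS to stratification.

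**The sevenfold dilution is an extreme case.** It assumes no difference at any other visit, including C6D1. That is why both patterns are shown. It also stands that the visit schedule limits any model: only one of five maintenance courses has an on-therapy questionnaire soon after it.

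**Conclusion.** The concern holds in this form: the only between-arm PRO model heavily dilutes a transient maintenance effect and misplaces a sustained one in time. The fitted share at week 16 is about 0.14 of a C5D1-only difference and 0.53 of a difference that lasts from C5D1 onward, the latter overstated to 1.29 at week 96. Which pattern is nearer the truth is unknown, and effect sizes, SDs, variance components and attrition are assumptions. The strata omission is separate and small.

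Two caveats apply. Gaps are as scheduled; the ±7-day windows and BCG delays will shift them. For re-induced participants C5D1 falls within the suggested re-induction course, and their nearest on-therapy visit after maintenance is C10D1, at 70 days.

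The reasoning also relies on Arm B having no maintenance BCG. The intervention table in Protocol 6.1 lists maintenance days in the Arm B column, whereas Section 4.1.1 defines Arm B as induction only. These passages must be reconciled.

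**What to change.** Replace the main PRO model in SAP 6.3.1.6 with a mixed model for repeated measures: scheduled visit as a categorical factor, treatment, treatment-by-visit interaction, baseline score, CIS and geography, with a prespecified fallback covariance structure.

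- Report all pairwise contrasts by visit in all randomized participants with PRO data.
- Name A vs B at C5D1 as the contrast that isolates maintenance BCG. B vs C also differs by PF-06801591, and A vs C share the maintenance schedule.
- Treat any analysis excluding re-induced participants as descriptive, because re-induction is a post-randomization event.
- State whether the EOT questionnaire enters the model.
- Keep the random coefficient model as supportive.
- If PRO results by arm have already been seen, label the new model post hoc.

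The cost is SAP text and a different model call on data already collected. The downside is more parameters and possible convergence problems, which the fallback covariance addresses.

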AE: adverse event, ACTH: adrenocorticotrophic hormone, ADA: anti-drug antibodies; BCG: *Bacillus Calmette Guérin*, BP: blood pressure; CIS: carcinoma in situ; CT: computed tomography, ECG: electrocardiogram, ECOG PS: Eastern Cooperative Oncology Group Performance Status, EORTC-QLQ-C30: European Organisation for Research and Treatment of Cancer Quality of Life Questionnaire-30 (items); EOT: end of treatment; MRI: magnetic resonance imaging, NAb: neutralizing antibodies; NMIBC: non-muscle invasive bladder cancer, PGIC: Patient Global Impression of Change; PGIS: Patient Global Impression of Severity; PK: pharmacokinetics, PTAB: Patient Treatment Administration Burden; Q4W: every 4 weeks; TSQ: Treatment Satisfaction Questionnaire

End of Treatment Visit and Follow-Up Period – Cohort A

	EOT*	Post-Treatment Period			*EOT: End of Treatment visit will take place within 7 days of the last dose of PF-06801591 or BCG (whichever is later) or decision to discontinue both drugs. This includes participants that complete the full 25 cycles of treatment as well as participants that discontinue treatment early. **Safety Follow-Up: All participants enter safety follow-up period at EOT. Visits at 30, 60, and 90 days post-EOT. ***Disease Follow-Up: Participants with no recurrence of high-grade disease, disease progression, or persistence of CIS before EOT will be assessed Q12W for 2 years after randomization and Q24W thereafter until recurrence of high-grade disease or disease progression, consent withdrawal, lost to follow-up, or death. Timing of disease assessment is fixed according to the calendar, starting with randomization and should not be adjusted. ****Survival Follow-Up: Q12W until consent withdrawal, lost to follow-up, death, or end of study (5 yrs from last participant randomized). Sponsor may request that sites complete additional survival follow-up to facilitate planned analyses as needed.
		Safety Follow-Up **	Disease Follow-Up ***	Survival Follow-Up ****	
Visit Window (Days)	+7	±7	±7	±7	
Physical Examination	X	X			Physical examinations should be performed according to clinical practice. Any abnormalities should be recorded as adverse events. See Section 8.2.1.
Weight	X	X			
Vital Signs	X	X			BP and pulse rate will be performed. Any abnormalities should be recorded as AEs. See Section 8.2.2.
Contraception check	X	X			
ECOG PS	X				

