7. DISCONTINUATION OF STUDY INTERVENTION AND PARTICIPANT DISCONTINUATION/WITHDRAWAL

7.1. Discontinuation of Study Intervention

For participants in Cohort A, it may be necessary for a participant to permanently discontinue one of the two study interventions. In that case, please note that the participant will still continue with the other study intervention. If it is necessary for the participant to permanently discontinue both PF-06801591 and BCG, the participant will remain in the study and move into the post-treatment follow-up period to allow for an adequate evaluation of the study objectives based on the prespecified estimands.

Note that permanent discontinuation of study treatment does not represent withdrawal from the study.

Participants may withdraw from study treatment at any time at their own request, or they may be withdrawn at the discretion of the investigator or sponsor for safety or behavioral reasons, or the inability of the participant to comply with the protocol-required schedule of study visits or procedures at a given study site.

Reasons for withdrawal of study treatment in Cohorts A, B1, and B2 may include:

- Completion of study treatment (25 cycles for Cohort A, Arms A, B and C, and Cohort B1, and 17 cycles for Cohort B2)
- Participants with CIS at baseline who do not achieve a CR within 6 months of initiating study intervention will be withdrawn from study treatment
- Recurrence of high-grade disease (Section 10.9) or progression of disease
- Global deterioration of health status requiring discontinuation of study treatment
- Unacceptable toxicity
- Pregnancy
- Significant protocol violation
- Lost to follow-up
- Participant refused further treatment
- Study terminated by sponsor
- Death

Discontinuation of study treatment for abnormal liver function should be considered by the investigator when a participant meets one of the conditions outlined or if the investigator believes that it is in best interest of the participant. See Section 10.6 for details.

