##### **Start and end dates of study treatment:**

For Arm A and Arm B in Cohort A:

The date/time of first dose of study treatment in a combination arm is the earliest date/time of the first non-zero dose date/time for any of the study drugs in the combination.

The date/time of last dose of study treatment in a combination arm is the latest date/time of the last non-zero dose date/time for any of the study drugs in the combination.

For Arm C (BCG only) in Cohort A and Cohorts B1 and B2 (PF-06801591 only):

The date/time of first dose of study treatment is the earliest date/time of non-zero dosing of the study drug.

The date/time of last dose of study treatment is the latest date/time of non-zero dosing of the study drug.

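### The only between-arm PRO model ends at each participant's end of therapy, so after a permanent BCG stop it loses later scores in Arm C that it can keep in Arms A and B

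*SAP*

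**What the plan says.** SAP 6.3.1.6 fits random coefficient models to QLQ-C30, NMIBC24, the EQ-5D-5L index and the EQ-VAS. The predictors are the baseline score and "treatment, time (treated as a continuous variable), and treatment-by-time interaction", with a random intercept and slope per participant. The data window is one sentence: "All available data for each participant prior to the end of therapy should be used in the analyses". Neither that section nor the rest of SAP 6.3.1 says what date ends therapy. The remaining PRO analyses (completion rates, descriptive summaries, health-status counts, a disposition figure) are by arm and contain no between-arm model.

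Protocol 9.4.3.1 plans the same comparison: "Longitudinal mixed effect-model analyses will be used to assess change from baseline in the EORTC QLQ-C30 & NMIBC24 domains and EQ-5D-5L", across the three Cohort A arms. It states no data window.

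Three passages decide when therapy ends:

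- Protocol 7.1: if one of the two drugs must be stopped permanently, "the participant will still continue with the other study intervention".
- Protocol 1.3 (Schedule of Activities): the end-of-treatment visit takes place "within 7 days of the last dose of PF-06801591 or BCG (whichever is later) or decision to discontinue both drugs".
- SAP 3.4.1: "The date/time of last dose of study treatment in a combination arm is the latest date/time of the last non-zero dose date/time" for any drug in the combination. For Arm C it is the last BCG dose.

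**The concern.** The cut is worded identically for every arm, but the same clinical event triggers it in one arm and not in another. A participant who permanently stops BCG in Arm A stays on therapy through PF-06801591, so later questionnaires enter the model. The same participant in Arm C has reached the end of therapy and contributes nothing further.

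Protocol 2.3 says bladder irritability is commonly expected with BCG, and NMIBC24 carries a seven-item urinary symptom scale (protocol 8.1.2.2). Scores after a BCG stop may therefore differ from scores on BCG. If so, the A-versus-C contrast sets a course that includes observed off-BCG scores against one projected from on-BCG scores. Health-related quality of life is a stated secondary objective of Cohort A, and this model is its only formal comparison between arms.

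**Working it through.** The documents give no sample size, power or effect for the PRO model, so there is no stated figure to reproduce. The check has four steps.

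**1. What a permanent BCG stop does.**

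| | Arm A, or Arm B during induction, PF-06801591 continuing | Arm C |
|---|---|---|
| Drug remaining | PF-06801591 (protocol 7.1) | none |
| End-of-treatment visit | after the later last dose, or when both drugs stop | after BCG ends |
| SAP 3.4.1 last dose | latest dose of either drug | last BCG dose |
| Later scores in the model | yes | no |

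In Arm B, BCG ends after induction by design and PF-06801591 likewise carries therapy on.

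**2. Scheduled scores in the model.** The Cohort A Schedule of Activities places post-baseline QLQ-C30 and NMIBC24 on Day 1 of Cycles 2, 3, 4, 5, 6, 7, 10, 13, 19 and 25, which is 10 assessments. Week = 4 × (cycle − 1), so they run from week 4 to week 96.

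| BCG stops after | Arm C, cut at last dose | Arm A, PF-06801591 to Cycle 25 |
|---|---|---|
| Cycle 4 | 3 of 10 | up to 10 |
| Cycle 7 | 6 of 10 | up to 10 |
| Cycle 13 | 8 of 10 | up to 10 |

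The missing definition matters here. Maintenance courses after Cycle 7 are six cycles apart. If therapy ends only when the Cycle 13 course is declined, the Cycle 10 questionnaire (week 36) also counts and the Cycle 7 row becomes 7 of 10.

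**3. What is collected after a stop.** The post-treatment schedule marks QLQ-C30 and NMIBC24 at end of treatment, in safety follow-up and in disease follow-up. It marks EQ-5D-5L only at end of treatment and in safety follow-up. For a last BCG dose on Cycle 7 Day 15 (week 24 + 2 = 26), and taking end of treatment at that date, safety visits at 30, 60 and 90 days fall at weeks 26 + 30/7 = 30.3, 26 + 60/7 = 34.6 and 26 + 90/7 = 38.9. If questionnaires follow the 12-weekly disease assessments, weeks 36, 48, 60, 72, 84 and 96 add 6. That makes up to 3 + 6 = 9 collected assessments outside the model. The schedule does not state PRO timing within disease follow-up, so the 6 is an upper count.

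**4. Could it move the contrast?** All inputs in this step are assumed: no true arm difference; the same share stopping BCG at week 24 in Arms A and C; a symptom score 5 points higher up to week 24 in those who stop; three levels afterwards; independent random intercept SD 10 and slope SD 6 per 100 weeks; residual SD 10; no baseline covariate; no other dropout. With g indexing stoppers and non-stoppers and w their shares, the expected estimate in an arm is

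β = (Σ w_g X_g′V_g⁻¹X_g)⁻¹ Σ w_g X_g′V_g⁻¹μ_g

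and the week-96 contrast is (1, 0.96)·(β_A − β_C). With 10% stopping and a later level of 0, Arm A is −0.149 and Arm C is 0.426, so the contrast is −0.149 − 0.426 = −0.58. With all data in both arms it is 0.

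| Share stopping | Later level 0 | Later level −5 | Later level still +5 |
|---|---|---|---|
| 10% | −0.58 | −1.22 | +0.07 |
| 20% | −1.15 | −2.45 | +0.15 |
| 30% | −1.73 | −3.68 | +0.22 |

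If symptoms ease after the stop, the rule creates an apparent Arm A advantage. If they do not, the shift is near zero and changes sign.

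**The case against.** The best defence is that quality of life on assigned therapy is a legitimate question. An Arm A participant off BCG but on PF-06801591 is still on assigned therapy, and an Arm C participant off BCG is not. One rule applies to all arms, and a mixed model accommodates dropout that is predictable from observed scores. The first part stands, and it is why the on-treatment model should be kept. The second does not remove the problem: no off-BCG score from an Arm C stopper enters the model, so a change that begins with the stop cannot be learned from that arm's data.

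Several stronger readings are tempting and are not supported:

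- *Arm C stoppers leave the model.* They contribute no further data, but everything before the stop remains.
- *Post-treatment questionnaires go unused.* This is true of this model only. SAP 6.3.1.4 summarises scores at each time point by arm.
- *The SAP contradicts the protocol.* Protocol 9.4.3.1 is silent on the window, protocol 9.4 calls itself a summary, and the SAP may add detail. Its absence from the list of changes in SAP 2.1 is editorial.
- *Stops for recurrence add to the imbalance.* Recurrence or progression leading to discontinuation, and persistent CIS, end therapy in every arm.

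**Conclusion.** The point holds for permanent BCG stops while PF-06801591 continues. The only between-arm PRO model then loses later scores in Arm C that it can retain in Arms A and B: about 6 or 7 of 10 scheduled assessments against up to 10 for a stop after Cycle 7. This rests on reading end of therapy as each participant's own end of all study treatment, which is the natural reading but is not stated.

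A reader might infer that the quality-of-life comparison is biased towards Arm A by a known amount. The documents do not support that. They give no BCG stopping rate, no reasons for stopping and no PRO effect. The shifts of about −3.7 to +0.2 points shown above depend wholly on assumed inputs. Nor is it shown that the on-treatment model is wrong as such. The PRO endpoints lie outside the alpha-controlled hypotheses H01 to H04, so no decision rule of the trial is affected. The change is worth making because it bears on a secondary objective and uses data already scheduled.

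**What to change.** 1. Define end of therapy in SAP 6.3.1.6: last dose of any study drug, or decision to stop all of them.
2. For QLQ-C30 and NMIBC24, fit the same random coefficient model to all collected questionnaires regardless of treatment stop. Use one window from randomization that is identical in every arm, for example through week 96, with any safety or disease follow-up questionnaires that fall inside it.
3. Report this beside the on-treatment model, and interpret the arm contrast only with both.
4. For EQ-5D-5L, run the same all-data model, but state that the imbalance cannot be fully removed. An Arm C participant who stops BCG early has no scheduled EQ-5D-5L after the 90-day safety visit, while the Arm A counterpart continues to Cycle 25. That gap lies in collection, not analysis.

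The cost is SAP wording and one extra model run per scale on existing data. Two limits remain: post-treatment scores may fit the linear time term less well, and participants who move to telephone survival follow-up after recurrence, persistence or progression will add little.
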